5.6.2 Follow-up procedures

Follow-up 10 to 14 days after study entry

At the follow-up visit the following will be done:

- Physical examination, including weight and height or length.
- A rectal swab or stool sample culture for the isolation of *V cholerae*.
- *Salmonella*, *Shigella* and *Campylobacte* cultures will be done on patients who are symptomatic at the follow-up visits.
- A detailed examination of gait and joints, to include ankles, knees, hips, shoulders, wrists and elbows and also any other symptomatic joint.

Follow-up 4 to 6 weeks after study entry

- Recording of adverse events.
- A rectal swab or stool sample culture for the isolation of *V cholerae*.
- *Salmonella*, *Shigella* and *Campylobacte* cultures will be done on patients who are symptomatic at the follow-up visits.
- A detailed examination of gait and joints, to include ankles, knees hips, shoulders, wrists and elbows, and also any other symptomatic joint.

Long-term follow-up

Patients who develop joint changes during therapy or during the follow-up period should be followed up until:

- (a) The averse event has resolved
or
- (b) Until a further change in the patient's condition is unlikely and a final causality assessment has been made. This may be shorter or longer than 3 months from the time of discharge.

Any new objective finding noted on clinical joint or gait assessment will be thoroughly evaluated by the investigator. This evaluation may include diagnostic procedures, such as an MRI and/or joint fluid assessments, as appropriate.

5.7 Subject's compliance

The oral study drugs will be administered in the Study Ward of the Clinical Research Centre of ICDDR,B. by study nurses. The prescription chart and the drug inventory log will provide documentation of preparation and administration of the study treatment. Patients randomised to the erythromycin arm must take at least 10 doses of erythromycin medication. Patients assigned to the ciprofloxacin arm must take the single dose of ciprofloxacin in order to be considered compliant with the protocol. Non-compliance will also be considered if two consecutive doses of the study medication are missed by a patient.

5.8 Concomitant therapy

All concomitant medication will be recorded in the case report form. Information recorded will be the name of the drug(s), individual, daily and total dose (or range of doses) received, and dates of administration.

5.8.1 Medication not allowed

Concomitant treatment with warfarin (or products containing coumarin derivatives), theophylline, non-steroidal anti-inflammatory drugs or cyclosporin will be avoided, except when such therapy is indicated and appropriate monitoring as well as laboratory investigations have been done. Concomitant treatment with glibenclamide and probenecid should also be avoided.

Concomitant treatment with oral/parenteral antimicrobial agents must be avoided. Patients who receive concomitant antimicrobials will be considered protocol violators and will be invalid for analysis of efficacy. However, should concomitant antibiotic therapy be initiated for the primary illness on the basis of clinical necessity, although unlikely, the patient will be assessed as a treatment failure.

Treatment with iron, sucralfate or antacids and highly buffered drugs containing magnesium, aluminium or calcium reduce the absorption of ciprofloxacin and should be avoided.

5.8.2 Medication allowed

Paracetamol may be used for control of fever, although this will be unlikely in association with cholera. The proportion of patients who may require paracetamol in the two treatment groups will be compared during analysis.

Ciprofloxacin should be administered either 1 to 2 hours before or at least 4 hours after administration of antacids, iron, sucralfate and highly buffered drugs containing magnesium, aluminium or calcium.

5.9 Removal of subjects from trial

It is the responsibility of the investigator to maintain the patients in the study. However, a patient may be withdrawn prematurely from the study for any of the reasons mentioned below. The reasons must be documented in the CRFs:

- Lack of clinical efficacy:
In the event no response to treatment (significant remission of clinical signs and symptoms) is observed, or if the clinical condition of the patient deteriorates within 48 hours of initiation of the study drugs, the study drug will be stopped and such patients will be treated with an effective alternative drug as described under Section 5.6.1, Reporting treatment failures.
- Significant adverse events and clinical deterioration:
In the event of a significant adverse event or deterioration in the clinical condition which would preclude further participation in the study, for example:
 - Serious toxic or allergic reaction.
 - Intercurrent diseases.
 - Aggravation of a concomitant disease.
 - Serious laboratory abnormality.
- Withdrawal of consent.
- Protocol violations.
- If the child vomits within 30 minutes of administration of study drug, any other treatment may be given and the patient will be withdrawn from the trial.

Procedures at premature termination of treatment

If a patient's clinical condition shows no sign of improvement or deteriorates 48 hours after initiation of the study drug, or if a patient develops a serious adverse event or allergic reaction, or if a superinfection develops, or if both the admission stool and rectal swab culture fail to grow *V. cholerae*, the study drug will be stopped and appropriate management will be instituted. However, before institution of any other antimicrobial agent such patients will be clinically evaluated and appropriate laboratory tests, including cultures, will be performed to ensure that the information required to evaluate the discontinued study drug therapy will be available and recorded on the CRFs. Patients who receive at least one dose of the study drug will be evaluated for safety. Every effort will be made to follow-up such patients, including patients who are dropped from the study for any reason. Trained health workers will be sent to locate patients who fail to show up for the follow-up assessments at their homes. Parents will be encouraged to comply with the follow up visit.

Follow-up procedures for patients prematurely withdrawn from the study

All patients who receive the study drug should be followed-up for 10 to 14 days after study entry. This should be done even if no adverse events or abnormal laboratory values are evident during hospitalisation. As indicated above, patients who develop any adverse event will be closely observed until the effect is reversed, or until a further change in the patient's condition is unlikely, and after a final causality assessment has been made. If a patient discontinues participation in the study for any reason, a final evaluation will be made at the time of discontinuation or as soon as possible thereafter. The results of the final assessment, and the reasons for discontinuation of study drug, will be recorded in the CRF. In the event of premature termination of study due to an adverse event, the procedure as described in Section 5.3 will be followed. Study patients presenting with adverse events, including clinically relevant laboratory

test abnormalities, will be followed-up by the investigator. Assessments must be made of the seriousness, intensity and relation to the administration of the trial medication.

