5.1 Overall design and plan of trial

This is a randomised, open, parallel group clinical trial to compare the efficacy and safety of a single dose of ciprofloxacin oral suspension 20 mg/kg with a 3-day course of erythromycin oral suspension administered in a dose of 12.5 mg/kg every 6 hours (12 doses) in the treatment of children, aged 2 to 15 years, with clinically severe cholera due to *V. cholerae* O1 or O139.

The sample size of the study has been determined to include 80 valid patients in each of the two treatment groups, i.e. a total of 160 patients. It is estimated that approximately 180 children, fulfilling eligibility criteria, will be initially enrolled to ensure the desired sample size.

Eligible patients will be admitted to the Clinical Study Ward of the Dhaka and Matlab Hospitals of ICDDR,B. Upon admission, their weight (dehydrated weight) and vital signs will be recorded, and a thorough physical examination including assessment of dehydration (following WHO guidelines) will be made. Patients will then be rehydrated using intravenous Dhaka Solution (133, 13, 98 and 48 mmol/l of sodium, potassium, chloride and bicarbonate respectively) over 3-4 hours. Thereafter, they will be observed over a 4-hour Observation Period when their hydration will be maintained using the rice-based ORS (containing 3.5, 2.5, 1.5 and 50 gram/l of sodium chloride, sodium bicarbonate, potassium chloride and rice powder). Dhaka Solution, as used for initial rehydration, will be used for patients whose hydration cannot be maintained by rice-based ORS.

Patients who have a stool output of 20 ml/kg or more during the Observation Period, and who have *V. cholerae* demonstrated in dark-field microscopic examination of their stool sample, will be enrolled upon obtaining written informed consent of their parents or guardians. If possible, assent must be obtained from the child. Patients will then be randomly assigned to receive one of the two treatment regimens.

Children will be hospitalised for 5 days or until resolution of their diarrhoea whichever is longer, and they will be asked to return for a follow-up evaluation 10 to 14 days after study entry. Patients are to return for a further follow-up visit at 4 to 6 weeks (Day 28 to Day 42).

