5.3 Method of assigning subjects to trial groups and blinding procedure

Patients eligible for participation in this study will be randomly assigned to one of the two treatments.

"Code break cards" will be prepared, and will be retained by the investigator. Once, and only once a patient's eligibility for the study has been confirmed, the investigator will open the code break card with the lowest available number and allocate the patient to the treatment specified in the code break card.

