5.10.2 Trial objectives

The aims of this study are to investigate the efficacy of a single dose of ciprofloxacin oral suspension in comparison to erythromycin oral suspension for treatment of severe cholera in children due to *V. cholerae* O1 or O139, and to evaluate the safety (particularly musculoskeletal safety) of the drug.

Criteria for Evaluation of Study Objectives

As measures of effectiveness, the primary and secondary outcome measures will be compared.

Primary outcome measures

- Rates of clinical success at test of cure visit.

Secondary outcome measures

- Rates of bacteriologic success at test of cure visit.
- Duration of diarrhoea.
- Rates of clinical relapse.
- Rates of bacteriological relapse.
- Duration of faecal excretion of *V. cholerae* O1 or *V. cholerae* O139.
- Measurements of six-hourly volume of watery stool will be done for the period in which patients are hospitalised.
- Proportion of patients requiring unscheduled intravenous fluids.
- Frequency of vomiting and its volume
- Frequency of stool per day.
- Frequency of vomit per day.
- Safety.

Ciprofloxacin concentrations will be determined for both stool and serum. Stool will be collected in six-hourly for the first 72 hour of the study (thus 12 stool samples per patient). Blood samples will be taken from each patient during one of four time periods; before drug administration; within 1 hour of first drug administration; 1-2 hours after first drug administration; and 4-12 hours after the first dose. A 1-ml sample will be required at each time window.

Definitions

Response to therapy will be evaluated at test of cure visit (Day 5).

Test of cure (End of Day 5)

The clinical response will be defined as:

- **Clinical success:** cessation of watery stool within 48 hours of administration of the study drug without recurrence by Day 5.
- **Clinical failure:** continuation of watery stool for > 48 hours, or initial cessation with recurrence on or before Day 5.

The bacteriological response will be defined as:

- **Bacteriological success:** eradication of the infecting *V. cholerae* organism from faecal specimens within 48 hours of initiation of the study drug without its subsequent isolation by Day 5.
- **Bacteriological failure:** isolation of infective *V. cholerae* O1 or O139 from a faecal sample on Days 3, 4 or 5.

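### Section 5.9 words the lack-of-efficacy trigger in two ways, and a child rescued before 48 hours can count as a failure, a success or a per-protocol exclusion

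*Protocol*

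**What the plan says.** Protocol 5.9 addresses lack of efficacy twice. Its list of reasons for withdrawal begins "In the event no response to treatment (significant remission of clinical signs and symptoms) is observed" and continues "if the clinical condition of the patient deteriorates within 48 hours of initiation of the study drugs, the study drug will be stopped"; "such patients will be treated with an effective alternative drug as described under Section 5.6.1, Reporting treatment failures". The 5.6.1 text it points to gives no time or stool criterion and leaves treatment after a judged clinical failure to the investigator's discretion. Further down, under procedures at premature termination, the condition for stopping is "If a patient's clinical condition shows no sign of improvement or deteriorates 48 hours after initiation of the study drug".

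Section 5.8.1 makes patients who receive concomitant antimicrobials invalid for efficacy, with one exception: if an antibiotic is started for the primary illness out of clinical necessity, "the patient will be assessed as a treatment failure". No time is attached.

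Section 5.10.2 defines clinical success as watery stool stopping within 48 hours of the study drug and not recurring by Day 5. Clinical failure is "continuation of watery stool for > 48 hours, or initial cessation with recurrence on or before Day 5". Rescue is mentioned in neither definition.

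Section 5.10.1 expressly keeps treatment failures in the per-protocol (PP) set, but describes them as children with watery stool for more than 48 hours. A valid course requires the single ciprofloxacin dose or at least 10 erythromycin doses.

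On blinding, 5.1 states "This is a randomised, open, parallel group clinical trial to compare the efficacy and safety", and under 5.3 "the investigator will open the code break card with the lowest available number and allocate the patient to the treatment specified".

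**The concern.** The primary endpoint gives every child 48 hours for watery stool to stop. Section 5.9 allows a child to be taken off study treatment and given another antibiotic inside that window, in words that do not match its own later paragraph. The sections that should then say how the child counts disagree. One calls the child a failure, one defines failure in terms the child may not meet, and one may remove the child from the PP set in one arm only.

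At stake is the primary comparison, a difference in clinical success rates judged against a 15-point margin. Where the stated rules allow more than one outcome for the same child, the choice falls to someone who knows the treatment given. In a non-inferiority trial the PP set matters alongside the ITT set, so a handling rule that works differently in the two arms needs to be closed before data are seen.

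**Working it through.** **The plan's own figure.** Inputs from 9.1: success rates 0.85 (ciprofloxacin) and 0.80 (erythromycin), margin 0.15, two-sided 5% (one-sided 2.5%), power 90%. The Farrington-Manning formula is n = [(z₀.₉₇₅·s₀ + z₀.₉₀·s₁)/(P_T − P_R + 0.15)]². The restricted estimates are 0.7216 and 0.8716, so s₀ = √(0.7216×0.2784 + 0.8716×0.1284) = 0.559. For the alternative, s₁ = √(0.85×0.15 + 0.80×0.20) = 0.536. Then n = [(1.960×0.559 + 1.282×0.536)/0.20]² = 79.5, that is 80 per group, as stated. The sample size is not in question.

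**One child followed through the rules.** Take a child who deteriorates before 48 hours, is given another antibiotic, and whose watery stool then stops by 48 hours without recurrence by Day 5.

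- *5.9, list of reasons:* stopping and switching is permitted.
- *5.9, procedures paragraph:* the stated trigger, 48 hours after initiation, has not been reached.
- *5.8.1:* treatment failure.
- *5.10.2:* the wording for success is met, and neither limb of failure is met.
- *5.10.1, ITT:* included, but as success or failure depending on which of the two preceding sections is applied.
- *5.10.1, PP:* the sentence that retains failures does not describe this child, so inclusion turns on the valid-course criteria, including the dose count.

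**Dose count by arm.** With 6-hourly dosing from hour 0, the erythromycin doses before 48 hours fall at 0, 6, 12, 18, 24, 30, 36 and 42 hours, which is 8. The 10th falls at 9 × 6 = 54 hours. An erythromycin child stopped before 48 hours cannot reach 10 doses. A ciprofloxacin child meets the dose rule with the single dose. Section 5.10.1 excuses other antimicrobials after a declared clinical failure, and missing test-of-cure data after an earlier failure. It does not excuse the dose rule.

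**Illustrative size, 80 evaluable children per arm.** At the planned erythromycin rate there are 0.80 × 80 = 64 successes. For one such child:

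| Handling | Arm rate | Change |
|---|---|---|
| Success | 64/80 = 80.0% | – |
| Failure, kept in the set | 63/80 = 78.75% | 1.25 points |
| Excluded from PP | 63/79 = 79.7% | about 0.25 points |

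In the ciprofloxacin arm, rescoring one child likewise moves the rate by 1/80 = 1.25 points. Against the margin, 1.25/15 is one twelfth per child. The number of such children is not in the documents.

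**The case against.** The strongest reply is that the two paragraphs of 5.9 can live together. One lists reasons for which a patient may be withdrawn, and the other says what to do at termination. An early stop for deterioration and a 48-hour stop for non-improvement are not mutually exclusive. Section 5.8.1 already gives the rescued child an outcome, and 5.10.1 foresees an earlier treatment failure. Reasons for withdrawal go into the CRF (5.9), stool volume is measured every 6 hours (5.6.1), and withdrawals are reported by group (9.3). Section 5.8.1 itself calls such rescue unlikely.

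Much of this stands, and it rules out several stronger inferences:

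- A reader might infer that the no-response limb has no time limit, so that a child merely still purging at 24 to 36 hours may be switched. The 48 hours can be read as governing both limbs; only the deterioration limb clearly allows an earlier switch.
- A reader might infer that the second paragraph keeps a child on study until 48 hours. It does not forbid an earlier stop.
- A reader might infer that scoring rescue as failure is wrong, or falsely lowers a success rate. It is a common and defensible rule, and what the child would have done without rescue cannot be observed.
- A reader might infer that switching will depend on the arm. The trial is open and nothing prevents it, but no text shows it or gives it a direction.

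The reply does not make 5.8.1 and 5.10.2 agree on the rescued child, and it does not resolve the 10-dose rule. Both are in the protocol. An analysis plan can supply the extra table, but it cannot decide which bedside wording applies.

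**Conclusion.** The point holds as a conflict between stated rules that touches the primary endpoint. Section 5.9 words its trigger in two ways. The first permits rescue before 48 hours, at least for deterioration, and 5.8.1, 5.10.2 and the PP text do not give that child one outcome. PP handling can differ by arm because the 10-dose rule is out of reach for an erythromycin child stopped before 48 hours.

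The arm difference in PP assumes that dosing starts at hour 0 and keeps to the 6-hourly schedule, and that the child's watery stool does not go on beyond 48 hours (otherwise the retention sentence applies). The 1.25 points per child assume 80 evaluable children in the arm and that the child stays in the denominator. Neither the size nor the direction of any bias can be taken from the documents, so no change in type I error or power is claimed.

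**What to change.** Reconcile the two paragraphs of 5.9 with each other and with 5.8.1, 5.10.1 and 5.10.2, including the same text in the protocol outline. Which clinical rule should apply is for the sponsor and investigators; this review takes no position on it.

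Then state one outcome for a child rescued before 48 hours, identical in both arms and in both the ITT and PP sets, and say how the erythromycin dose rule applies to that child. Counting rescue as failure would be acceptable if 5.10.2 says so.

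Record the clock time of the switch: 5.8 asks for dates of administration, which cannot place a switch before or after 48 hours. Reasons and 6-hourly stool volumes are already collected. Report by arm the number of failures arising from a switch before 48 hours, with a sensitivity analysis of the primary difference, for example scoring these children once by the rescue rule and once by the watery-stool criterion alone. That table can sit in the analysis plan.

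The cost is an amendment of wording, one CRF field and one table. No new clinical measurement and no change in sample size is needed.

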5.10 Criteria for evaluation of trial objectives and safety

5.10.1 Description of subject groups for analysis

Safety analysis population

Patients will be included in the safety analysis if they receive at least one dose of study treatment.

ITT analysis population

Patients will be included in the ITT analysis if they have been diagnosed with cholera due to *V. cholerae* O1 or O139 and have received at least one dose of study treatment. Patients regarded as treatment failures, as discussed above, will be included in the ITT analysis.

PP analysis population

Patients will be included in the PP analysis if they satisfy the criteria for a valid course. Patients regarded as treatment failures (continuation of watery stool for > 48 hours) will be included in the PP analysis.

Definition of a valid course

For a course of therapy to be valid for evaluating the efficacy of treatment, the following criteria must be met and documented in the CRF:

- *V. cholerae* O1 or O139 must have been isolated from either the stool or rectal swab culture performed before initiation of the study drug on the day of admission (pre-therapy).
- No other systemic antimicrobial agent must have been administered concomitantly with the study drug unless it is done consequent to declaration of “clinical failure”.
- Documented adequate compliance with administration of the single ciprofloxacin dose, or at least 10 doses of the erythromycin medication. Non-compliance will also be considered if two consecutive doses of the study medication are missed by a patient.
- No protocol violations influencing the treatment efficacy.
- The patient must have met the inclusion/exclusion criteria.
- Efficacy data from the test of cure visit is available, unless there has been an earlier treatment failure.

Pharmacokinetic population

Ciprofloxacin concentrations will be determined in the first 20 patients aged 2-5 years, and in the first 20 patients aged > 5 years who enter the study. Ciprofloxacin concentrations will also be determined in all patients who vomit within 30 minutes of receiving their first dose of medication.

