9.1 Sample size estimation

The primary efficacy variable is the clinical response of the patient. The aim of the study is to show that single-dose therapy with ciprofloxacin oral suspension (test treatment) is at least as effective as the 3-day treatment regimen with erythromycin. The anticipated cure rate for ciprofloxacin is at least 0.85, and for erythromycin at most 0.80. The statistical hypothesis and alternative are:

$$H_0 : P_T - P_R < -0.15$$

$$H_a : P_T - P_R \geq -0.15$$

Rejection of the hypothesis allows one to conclude that the cure rate P_T for the test treatment is at most 15% less than the cure rate P_R of the reference treatment.

Given these assumptions and hypotheses, a power of 90%, and a two-sided significance level of 5%, a sample size of $N = 80$ patients per group are required to reject the above hypothesis (Farrington CP, Manning G. Statistics in Medicine 1990: 1447-1454). Assuming an invalidity rate of 10%, a total sample size of 180 patients is required.

Pharmacokinetics

The first 20 patients aged 2 to 5 years and the first 20 patients, aged > 5 years who enter the study will be evaluated for PK.

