9.4 Efficacy analysis

The efficacy variables (clinical and bacteriological response at test of cure visit) will be listed for all patients. The two treatment groups will be compared by calculating the Mantel-Haenszel point estimate and 95% confidence interval for the difference in success rates (clinical and bacteriological). For the single dose treatment with ciprofloxacin oral suspension to be declared at least as effective as the 3-day treatment with erythromycin oral suspension the lower bound of the 95% CI for the difference in clinical success rate at test of cure must be ≥ -0.15 (-15%).

The secondary efficacy variables will be listed for each patient, with descriptive statistics for each treatment group. With regard to duration of diarrhoea, the treatments will be compared using the log-rank test, and Kaplan-Meier curves will be presented, if appropriate, otherwise the data will be analysed descriptively using median duration. The stool and vomit volumes, proportion of patients requiring unscheduled intravenous fluids, and frequency of vomiting will be compared descriptively.

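### Section 5.9 does not separate stopping study drug from leaving the trial, and does not expressly carry stool records, swabs and the Day 5 assessment on for withdrawn children who remain in the ITT set

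*Protocol*

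**What the plan says.** Section 5.9 (Removal of subjects from trial) states that "a patient may be withdrawn prematurely from the study for any of the reasons mentioned below". The reasons are lack of efficacy, significant adverse events (with serious laboratory abnormality as an example), withdrawal of consent, protocol violations, and vomiting within 30 minutes of a dose. Sections 5.1 and 5.2.4 add withdrawal from the trial under the 24-hour creatinine rule.

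For a child who discontinues participation for any reason, "a final evaluation will be made at the time of discontinuation or as soon as possible thereafter". The next sentence of 5.9 has the CRF record why the study drug was discontinued, so the two events are treated as one. Section 5.9 also requires clinical evaluation and cultures before another antimicrobial is given, efforts to trace children dropped from the study, and follow-up of all dosed children for 10 to 14 days after entry.

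Section 5.10.1 sets no completion requirement for ITT: "Patients will be included in the ITT analysis if they have been diagnosed with cholera" due to O1 or O139 and have had at least one dose. Section 5.10.2 defines clinical success as "cessation of watery stool within 48 hours of administration of the study drug without recurrence by Day 5". Bacteriological success requires eradication within 48 hours and no later isolation by Day 5.

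**The concern.** The ITT set and the withdrawal procedure do not fit together. A child dosed and then withdrawn for an adverse event, a laboratory value, a protocol violation or early vomiting still counts in ITT if cholera is confirmed. Success for that child cannot be read from an evaluation at the moment of stopping, because it depends on whether watery stool had ceased by 48 hours and stayed away to the end of Day 5. The later follow-up visit defined in 5.6.2 (examination and culture) cannot reconstruct that course.

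The loss need not be balanced. Later doses can be stopped or missed only in the 12-dose erythromycin arm, and the trial is open, so withdrawal decisions are made with the arm known. Duration of diarrhoea is exposed too: if recording ends when a child who is still purging is withdrawn, that child's time to cessation is unknown for a reason linked to the outcome.

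This is a matter of data collection. An SAP can set rules for missing outcomes, but it cannot create observations that were never made.

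**Working it through.** **1. Which withdrawn children already have a primary outcome?**

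| Reason for stopping or withdrawal | Primary outcome fixed without Day 5 data? | Source |
|---|---|---|
| Lack of efficacy (watery stool beyond 48 h) | Yes, failure; kept in ITT | 5.10.1, 5.10.2 |
| Antibiotic started for the primary illness | Yes, failure | 5.8.1 |
| Adverse event or laboratory abnormality, including the creatinine rule | Not fixed | 5.9, 5.1, 5.2.4 |
| Protocol violation | Not fixed | 5.9 |
| Vomiting within 30 minutes | Not fixed; 5.4.1 calls the child invalid for efficacy, but 5.10.1 admits the child to ITT | 5.4.1, 5.9, 5.10.1 |
| Admission cultures negative | Not in ITT | 5.9, 5.10.1 |
| Consent withdrawn | Not fixed, but further data may not be obtainable | 5.9 |

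The gap is the third to fifth rows.

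**2. The plan's own sample size.** Inputs from 9.1: "The anticipated cure rate for ciprofloxacin is at least 0.85, and for erythromycin at most 0.80"; margin 0.15; 90% power; two-sided 5% (one-sided 2.5% against the margin). The Farrington-Manning restricted rates are 0.7216 and 0.8716.

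n = [1.960·√(0.7216·0.2784 + 0.8716·0.1284) + 1.282·√(0.85·0.15 + 0.80·0.20)]² / 0.20² = 79.5, so 80 per group, with power 90.2%. Then 160/0.9 = 177.8, or 178; the plan states 180. The figures reproduce, and the proposed change leaves them as they are.

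**3. How much could missing outcomes matter?** The documents give no number, so the following is assumed: 90 ITT children per arm, success of 0.85 and 0.80 among those observed, k missing per arm, and an unpooled Wald limit:

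L = (pT − pR) − 1.96·√[pT(1−pT)/90 + pR(1−pR)/90].

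Scoring against ciprofloxacin: pT = (90−k)·0.85/90 and pR = [(90−k)·0.80 + k]/90. Scoring in its favour: pT = [(90−k)·0.85 + k]/90 and pR = (90−k)·0.80/90.

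Example, k = 8, against ciprofloxacin: pT = 69.7/90 = 0.774; pR = 73.6/90 = 0.818; difference −0.043; standard error 0.060; L = −0.161.

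| k per arm | L, against ciprofloxacin | L, in favour |
|---|---|---|
| 0 | −0.061 | −0.061 |
| 3 | −0.099 | −0.031 |
| 5 | −0.124 | −0.012 |
| 7 | −0.149 | +0.008 |
| 8 | −0.161 | +0.018 |
| 9 | −0.173 | +0.028 |

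The −0.15 limit is crossed only from 8 per arm, and only when all unknowns in one arm are failures and all in the other are successes.

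**4. Unequal loss.** With 9 missing on erythromycin only, scoring them all as failures gives pR = 64.8/90 = 0.72 and a difference of +0.13 (L = +0.011). Scoring them all as successes gives pR = 73.8/90 = 0.82 and a difference of +0.03 (L = −0.078). Neither crosses −0.15, but the estimate moves by 10 points.

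**The case against.** The strongest reply is that 5.9 is silent and does not forbid measurement. Sections 5.6.1 and 5.10.2 tie rectal swabs, daily examination and 6-hourly stool volume to the hospital stay, not to being on drug. Every ciprofloxacin child is off drug after the single dose and is still measured. Section 5.1 plans a 5-day stay with no exception for withdrawn children, and follow-up for 10 to 14 days can be read as covering Day 5. This stands to the extent that a reader might infer that 5.9 collects only one evaluation, or that Day 5 data are lost by rule; the documents support neither. It does not close the gap. A child who is withdrawn from the trial is, on an ordinary reading, no longer under the trial schedule, and sites may differ. Staying on the ward is also not assured: 7.2 foresees some discharges before the end of the study.

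A reader might also infer that all children who stop early lack an outcome. That is too broad, as the first two rows of the table show.

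A third tempting step is to take the 10% in 9.1 ("Assuming an invalidity rate of 10%, a total sample size of 180 patients is required") as 9 missing outcomes per arm and conclude that they alone could decide non-inferiority. That figure is an allowance for invalid patients. It includes culture-negative children, who are not in ITT, and non-compliant or ineligible children, who may have full Day 5 data. Section 9.4 does not name ITT as the deciding set, and sections 5.1 and 5.2.2 size the trial on valid patients.

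Rules for imputation and censoring may sit in an SAP that is not shown, and they are not counted here.

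**Conclusion.** The point holds in a narrow form. Section 5.9 merges stopping the drug with leaving the trial and leaves it unstated whether stool records, swabs and the test-of-cure assessment continue. Confirmed, dosed children withdrawn for reasons other than efficacy failure may then have no ITT outcome, with possible imbalance between arms in an open trial. Lack-of-efficacy failures and children given an antibiotic for cholera are outside the gap for the primary endpoint.

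The size is unknown because the documents give no rate of missing Day 5 outcomes. Under the stated assumptions, a few missing per arm move the lower limit by several points but do not take it past −0.15. That takes about 8 or more per arm scored in opposite extremes, which is an outer bound. The change is worth making because it is cheap and because data not recorded during the stay cannot be recovered.

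**What to change.** In 5.9:

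- Distinguish study drug stopped from withdrawn from the trial, and reserve the latter for withdrawal of consent. This concerns data collection only and leaves the rules on when treatment stops as they are.
- State that for every dosed child the 6-hourly stool and vomit record, the daily rectal swab and the Day 5 assessment continue to the end of Day 5 unless consent is withdrawn.
- Record the time and reason of stopping, and any new antimicrobial with its start time.
- Use these data for the ITT clinical and bacteriological response and for duration of diarrhoea, keeping the 5.8.1 rule that an antibiotic started for the primary illness counts as failure. Without that rule, a child whose stools ceased on a replacement drug could be scored as a success.

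Separately, reconcile 5.4.1 (early vomiters invalid for efficacy) and 5.9 (withdrawn from the trial) with the ITT definition in 5.10.1.

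The cost is protocol wording, a few extra swabs, and CRF pages for children off study drug. Most of these children should still be inpatients under the planned 5-day stay. The sample size is unchanged.
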